A comparative analysis between College Park Sidekick Feet and conventional stubby prosthesis.

NCT02921295

Sep 27, 2016

Statistical Plan

A two-way analysis of variance (ANOVA) as a between subject variable and within subject variable will be used to analyze the dependent variable, completion time in seconds. A secondary analysis will observe additional dependent variables: cadence, velocity, step length, stride length, and pelvic girdle angles. The independent variables being analyzed include stubby feet compared with the Sidekicks and a level surface compared to gravel. The two-way ANOVA is used to determine whether there are any significant differences between the mean values of the independent groups. If a significant difference is detected an unpaired t-test will be implemented to determine if statistical significance exists. A probability value of 0.05 will be set at the level of statistical significance. Statistical analysis will be performed on SPSS software. The balance confidence scale and RPE scale will be compared across independent variables.

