A Comparative Analysis between Articulated and Conventional Stubby Prostheses

September 27, 2016

[name]

Study Protocol

A 10 meter walk test will be administered on a level sound surface and a gravel surface. The test will take place under four different conditions; 1) stubby prosthesis on level surface 2) stubby prosthesis on gravel surface 3) sidekick prosthesis on level surface 4) sidekick prosthesis on gravel surface. Each trial will be performed 3 times and the completion times will be averaged. There will be a 2-minute break between each 10-meter test and a 30-minute break when changing the feet style. During the 30-minute break the participant will change from the conventional stubbies to the sidekicks and the proper resistance will be set. The participant will be given about 20 minutes to rest and 10 minutes to walk around with the new feet style. The participant will walk a total of 10 meters. The intermediate 6 meters will be measured to allow for acceleration and deceleration. The participant will be instructed to walk at a comfortable, leisure speed.

A gravel surface will be constructed using a tarp and gravel. This surface will be used as an uneven surface in comparison to a level ground surface for the 10 meter walk test.

The TUG test will be performed on just the level surface using a standard chair with arm rests. The participant will begin seated in a chair. A piece of tape is placed 3 meters away, clear for the participant to see seated in the chair. On the word "GO" the participant will stand up, walk to the line on the floor, turn around and sit back in the chair. Time will be recorded from the word "GO" until the participant are seated, with the participant's back firmly against the chair. The participant will be wearing the G-Walk technology to analyse the movement at the pelvis. Three trials will be performed using each foot type and the participant will receive a 5 minute rest between the individual trials and a 10 minute rest between the foot change.

The G-walk technology is a Bluetooth wireless system that is worn around the waist with an ergonomic belt allowing the participant to move freely without any restrictions.

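### The SAP does not name the foot-by-surface interaction and closes on an unpaired two-mean t-test, which can neither confirm nor estimate it

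*SAP*

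**What the plan says.** **Design.** The Study Protocol crosses foot type with surface for the 10 meter walk: "The test will take place under four different conditions; 1) stubby prosthesis on level surface 2) stubby prosthesis on gravel surface", followed by the Sidekick on the same two surfaces. One person supplies all four cells: "During the 30-minute break the participant will change from the conventional stubbies to the sidekicks and the proper resistance will be set". The purpose of the gravel walkway is given in one sentence: "This surface will be used as an uneven surface in comparison to a level ground surface for the 10 meter walk test".

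**Analysis.** The Statistical Plan opens with "A two-way analysis of variance (ANOVA) as a between subject variable and within subject variable will be used to analyze the dependent variable, completion time". It lists the factors ("The independent variables being analyzed include stubby feet compared with the Sidekicks and a level surface compared to gravel") and states the aim: "The two-way ANOVA is used to determine whether there are any significant differences between the mean values of the independent groups". The follow-up is "If a significant difference is detected an unpaired t-test will be implemented to determine if statistical significance exists". The threshold is "A probability value of 0.05 will be set at the level of statistical significance".

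**Not stated.** Neither document mentions an interaction, says which means the t-test compares, or gives a sample size, SD, effect size or within-person correlation.

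**The concern.** A 2 x 2 crossed design answers three questions: the average foot effect, the average surface effect, and whether the foot effect depends on the surface. The SAP names the first two. The third is what crossing the factors adds. Gravel being slower than level ground, averaged over feet, says nothing about either prosthesis.

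The follow-up step adds to the problem. A significant ANOVA result could come from foot, surface or their interaction, and the SAP makes the t-test the deciding step after it. A t-test compares two cells or two margins. A difference of differences involves all four cells, so a significant interaction F would be followed by a test that cannot address it.

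The closest a two-mean t-test comes to the question is one foot comparison on level ground and another on gravel. If one fell below 0.05 and the other did not, a reader could take that as evidence that the Sidekick's benefit depends on terrain. Comparing two p-values does not test that.

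**Working it through.** **Inputs from the documents.** Four foot-by-surface cells per participant; unpaired follow-up t-test; significance level 0.05. There is no power or sample-size figure to reproduce.

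**Assumed inputs.** Two-sided tests without multiplicity adjustment; n = 5, 10, 20; total SD 1 in each cell; the same correlation r between any two cells of one person, r = 0.5, 0.7, 0.9; foot effect 0.5 SD. Results are from 40,000 simulated trials per setting. All of them are illustrations.

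**Step 1: what each test addresses.** Let S and B be a participant's Sidekick and stubby times, with subscripts g (gravel) and l (level). The interaction contrast is

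D = (S_g − B_g) − (S_l − B_l).

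A one-sample t-test of D against zero is the 1-df interaction F of a fully within-subject ANOVA. A two-mean t-test uses only S_g against B_g, or S_l against B_l, or a pair of margins. None of these is D.

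**Step 2: discordant p-values when the benefit is equal.** If each per-surface test has power p and the tests are independent, exactly one is significant with probability 2p(1−p):

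- p = 0.2 or 0.8: 2 × 0.2 × 0.8 = 0.32
- p = 0.5: 2 × 0.5 × 0.5 = 0.50
- p = 0.9: 2 × 0.9 × 0.1 = 0.18

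These values depend on the power assumed. The simulation below uses the unpaired test that the SAP names, with a true benefit of 0.5 SD on both surfaces:

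| r | n = 5 | n = 10 | n = 20 |
|---|---|---|---|
| 0.5 | 0.114 | 0.207 | 0.401 |
| 0.7 | 0.080 | 0.144 | 0.344 |
| 0.9 | 0.045 | 0.064 | 0.222 |

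The range is 0.045 to 0.401, rising with n. As a check, at r = 0.5 and n = 20 the per-surface power is 0.287, and 2 × 0.287 × 0.713 = 0.409, close to 0.401. The within-subject interaction test rejects in 0.048 to 0.053 of trials when the benefit is equal.

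The low values at small n reflect weak tests. At r = 0.7 the unpaired per-surface power is 0.05, 0.09 and 0.24 for n = 5, 10 and 20, against 0.20, 0.44 and 0.78 if paired.

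The simulation does not apply the SAP's condition that the ANOVA be significant first. That condition can only lower these rates, and it leaves them unchanged if a clear surface effect satisfies it in every trial.

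**Step 3: power of the direct test.** With equal correlations, Var(D) = 4(1−r). At r = 0.7 this is 4 × 0.3 = 1.2, so SD(D) = 1.095. For an extra 0.5 SD effect on gravel, the noncentrality is 0.5√n / 1.095, or 1.02, 1.44 and 2.04 for n = 5, 10 and 20. Power, and the power if the four cells are analysed as independent groups:

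| n | within-subject | as independent groups |
|---|---|---|
| 5 | 0.13 | 0.02 |
| 10 | 0.25 | 0.03 |
| 20 | 0.49 | 0.08 |

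The choice of error term therefore matters. The SAP's mixed description, with its reference to independent groups, leaves that choice open.

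**The case against.** The strongest reply has four parts.

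- **The interaction is available.** A two-way ANOVA on crossed factors can produce it, and nothing in the SAP limits the model to main effects. A list of independent variables would not normally include an interaction. A reader might infer that the plan contains no valid test of it. The documents do not support that: fitted fully within subject, the ANOVA gives a valid interaction F. What stands is that the SAP does not name this test, leaves its error term contradictory, and follows it with one that cannot address the question.
- **No misuse is planned.** A reader might infer that p-values will be compared across surfaces. The SAP does not say that t-tests will be run by surface or that a surface-specific claim will be made; the t-test could equally compare foot margins. The misreading is possible, and the wording does not prevent it.
- **The objective is not stated.** Neither document hypothesises that the Sidekick helps more on gravel, and both titles describe a plain device comparison. This stands and limits the weight of the point. The crossed design nevertheless makes the question a natural one, and leaving it unspecified allows it to be taken up after the data are seen.
- **The discordance rate depends on assumptions.** It does. Higher rates arise at n = 5 and 10 with paired tests (0.32 and 0.49 at r = 0.7), but the SAP specifies unpaired ones. At n = 5 and r = 0.9 the unpaired rate, 0.045, is no higher than the nominal level.

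**Conclusion.** The point holds as a gap in pre-specification together with a follow-up test that does not fit the design. It does not show that the planned ANOVA cannot test the interaction, or that a wrong claim will follow.

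Its size can only be illustrated. With an equal true benefit of 0.5 SD, r from 0.5 to 0.9 and n from 5 to 20, significance on exactly one surface occurs in about 4 to 40% of trials with the SAP's unpaired test, against about 5% for the direct test. At the lower end the problem is lack of power more than false surface-specific findings. With a real sample size and SD the figures would change. The mismatch between a two-mean test and a four-cell contrast would remain.

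**What to change.** Amend the Statistical Plan as follows:

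1. Fit foot type and surface as fully within-subject factors, and remove the between-subject description and the reference to independent groups.
2. State whether a foot effect that differs by surface is a study question. Name the 1-df foot-by-surface interaction, or equivalently the one-sample t-test on each participant's difference of differences, as its test. Report the estimate in seconds with a 95% CI.
3. Base any claim that the foot effect differs by surface on that test alone, and not on a t-test of two means. Make any by-surface foot contrasts paired and secondary.
4. Report the foot effect averaged over surfaces whatever the interaction shows. Do not treat a non-significant interaction as evidence of equal benefit; the CI shows which differences remain plausible.

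**Cost.** The change is to SAP wording and the model specification. The four conditions are already measured and SPSS is already named, so no new data or software is needed. The price is fewer surface-specific claims and, in a small sample, low power for the interaction, which the report should acknowledge.

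### The SAP decides significance with an unpaired t-test on what it calls independent groups, although each participant is measured with both feet on both surfaces

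*SAP*

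**What the plan says.** **Design (Protocol, Study Protocol).** The 10 m walk is done with each foot type on each surface: "The test will take place under four different conditions; 1) stubby prosthesis on level surface 2) stubby prosthesis on gravel surface", then the same two surfaces with the Sidekick. One person uses both feet: "During the 30-minute break the participant will change from the conventional stubbies to the sidekicks". Each condition is walked three times and the times are averaged, which gives one value per participant per condition. For the TUG, "The TUG test will be performed on just the level surface" and "Three trials will be performed using each foot type". Neither document describes parallel groups.

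**Analysis (SAP, Statistical Plan).** The first step is a two-way ANOVA, described "as a between subject variable and within subject variable will be used to analyze the dependent variable, completion time in seconds". The factors named are foot type and surface, but the SAP does not say which is between-subject and which is within-subject. It says the ANOVA looks for "significant differences between the mean values of the independent groups". The second step is: "If a significant difference is detected an unpaired t-test will be implemented to determine if statistical significance exists". The significance level is 0.05; sidedness is not stated.

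**The concern.** The follow-up test treats stubby times and Sidekick times as if they came from different people. They come from the same people. A slow walker will tend to be slow in every condition, and a paired analysis removes that shared component from the error term. The unpaired test leaves it in.

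The SAP gives this second test the job of determining significance. A foot effect detected by a correct within-subject ANOVA could therefore be overturned by a test that discards the pairing. A non-significant result would be hard to interpret, because it might reflect only the wrong error term. Confidence intervals built on the same standard error would be too wide.

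The ANOVA sentence adds a second difficulty. The design has no between-subject factor, yet the SAP names one and speaks of independent groups. Two analysts could read that sentence and run different models.

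**Working it through.** **What the documents supply.** The within-person design, one averaged value per condition for the walk, the unpaired follow-up test and alpha 0.05. They give no sample size, SD, effect size or within-person correlation, so there is no planned figure to reproduce. Everything numerical below rests on assumed values: n = 5, 10 or 20 participants; rho = 0.3, 0.5 or 0.8; equal SDs in the two conditions; normal data; two-sided testing.

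**Step 1: standard errors.** For two conditions with common SD s:

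- true (paired) variance of the mean difference = 2s²(1 − rho)/n
- variance assumed by the unpaired test = 2s²/n
- ratio of standard errors, unpaired to paired = 1/sqrt(1 − rho)

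This gives 1/sqrt(0.7) = 1.20, 1/sqrt(0.5) = 1.41 and 1/sqrt(0.2) = 2.24. Unequal SDs reduce the ratio. At rho 0.8 and an SD ratio of 2 it is sqrt[(1 + 4)/(1 + 4 − 2 × 0.8 × 2)] = sqrt(5/1.8) = 1.67.

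**Step 2: power of the unpaired t-test when the paired test has 80%.** The effect is set by the noncentral t distribution; 100,000 simulated trials per cell.

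| rho | n = 5 | n = 10 | n = 20 |
|---|---|---|---|
| 0.3 | 82% | 73% | 70% |
| 0.5 | 69% | 58% | 54% |
| 0.8 | 28% | 15% | 10% |

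At n = 5 and rho 0.3 the unpaired test taken alone loses nothing, because its 2(n − 1) = 8 degrees of freedom, against n − 1 = 4, make up for the larger standard error. More than half the power is lost only above a rho of about 0.6 (n = 20) to 0.73 (n = 5).

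**Step 3: type I error of the unpaired test, nominal 5%, n = 10.** It is 2.3%, 1.0% and 0.06% at rho 0.3, 0.5 and 0.8. The paired test stays at about 5%.

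**Step 4: fixed effects at n = 10, paired versus unpaired power.**

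| rho | 1.0 SD | 1.5 SD |
|---|---|---|
| 0.3 | 66% vs 58% | 94% vs 92% |
| 0.5 | 80% vs 58% | 99% vs 95% |
| 0.8 | 99% vs 62% | 100% vs 98% |

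At rho 0.8 an effect of 0.63 SD gives 80% versus 15%. The loss is small for large effects.

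**Step 5: the ANOVA, if run as independent groups.** With four equally correlated conditions, the foot main effect has true variance s²(1 − rho)/n, while the independent-groups model assumes s²/n with 4(n − 1) degrees of freedom. The ratio of standard errors is again 1/sqrt(1 − rho). Power when the within-subject analysis has 80% (40,000 trials per cell):

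| rho | n = 5 | n = 10 | n = 20 |
|---|---|---|---|
| 0.3 | 87% | 76% | 72% |
| 0.5 | 76% | 61% | 56% |
| 0.8 | 34% | 17% | 11% |

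Under that reading, correcting the t-test alone would leave the same fault in the first step.

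**The case against.** The strongest reply is that the SAP does name a within-subject variable, so the ANOVA may respect at least part of the pairing, and the reference to independent groups may be loose wording. That is fair. What is established for the ANOVA is ambiguity; the wrong error term in Step 5 follows only on one reading. The reply does not help the follow-up test, which is explicitly unpaired.

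Several limits on the numbers also stand:

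- **Size is not demonstrable for this trial.** With no n, SD, effect or rho in the documents, nobody can show that the trial falls where the loss is severe. With low correlation or a large effect, little is lost. The case for correction rests on the mismatch with the design, not on a proven loss.
- **The plan has two steps.** Steps 2 to 4 describe the t-test alone. If a within-subject test must be significant first, power at n = 5 and rho 0.3 is about 73%, not 82%, so even there something is lost against 80%.
- **Direction.** The conservative direction holds for positive rho and one averaged value per participant per condition. The protocol states averaging for the walk, not for the TUG. If the three TUG trials were entered as separate observations, false positives could exceed 5%: about 12% assuming n = 10, a correlation of 0.95 between trials with the same foot and 0.5 between feet, though about 2% if the latter is 0.8.
- **Scope.** The SAP never names the TUG, so extending its t-test to the TUG is an inference.

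**Conclusion.** The concern holds. The protocol describes a fully within-person comparison and the SAP prescribes a test for independent samples. Followed exactly, the SAP gives a wrong standard error whenever the within-person correlation is not zero. This is an error in what is written, not a missing detail, and it sits in the test that the SAP uses to determine significance for completion time.

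Under equal SDs the standard error is overstated by 20% to 124% for rho from 0.3 to 0.8. The cost in power runs from nothing to most of it, depending on correlation, sample size and effect, none of which the documents give. For averaged walk times with positive correlation the harm is missed effects and over-wide intervals, not false claims of a difference. The ANOVA wording needs correcting with the t-test because, as it stands, it permits an analysis with the same fault.

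**What to change.** Amend the single SAP paragraph as follows:

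1. Specify a two-way repeated-measures ANOVA with foot (stubby, Sidekick) and surface (level, gravel) both as within-subject factors. Remove the mention of a between-subject variable and of independent groups. A mixed model with participant as a random effect would serve equally well.
2. Take the two main effects and their interaction directly from that model. Each factor has two levels, so a main effect needs no follow-up test.
3. Replace the unpaired t-test with paired t-tests for simple effects (foot difference on level and on gravel) and for the TUG foot comparison on the level surface. State that TUG trials are averaged to one value per participant per foot.
4. Report the mean within-person difference, Sidekick minus stubby, with its 95% confidence interval.

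Items 1 and 3 remove the error and item 2 drops a redundant test. Item 4 is good practice, and a multiplicity adjustment for the simple effects, such as Holm, is optional. The cost is three wording changes and a sentence or two on the TUG and the interval. The data and the SPSS software stay the same, and no added visits or participants are needed.

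### The follow-up t-test is not tied to the foot effect, so a surface difference alone can open unadjusted foot comparisons and their error rate is not the stated 0.05

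*SAP*

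**What the plan says.** The SAP's Statistical Plan names two factors: "The independent variables being analyzed include stubby feet compared with the Sidekicks and a level surface compared to gravel". It gives the ANOVA's purpose in general terms: "The two-way ANOVA is used to determine whether there are any significant differences between the mean values of the independent groups". The next sentence sets the follow-up: "If a significant difference is detected an unpaired t-test will be implemented to determine if statistical significance exists". The threshold is "A probability value of 0.05 will be set at the level of statistical significance".

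The SAP does not say which ANOVA effect (foot, surface or interaction) opens the follow-up, which cells the t-test compares, how many t-tests there are, or how multiplicity is handled.

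The protocol describes the walk test: "The test will take place under four different conditions", that is, each foot on each surface. The same person wears both feet: "During the 30-minute break the participant will change from the conventional stubbies to the sidekicks and the proper resistance will be set". The foot data are therefore paired.

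**The concern.** The purpose of the trial, by its title, is to compare the two prostheses. Surface is the other factor, and the sponsor builds the gravel surface so that walking on it can be set against level ground: "This surface will be used as an uneven surface in comparison to a level ground surface for the 10 meter walk test". If any significant effect is enough to start the t-tests, a surface effect that says nothing about the prosthesis licenses tests of the prosthesis. The ANOVA then gives the foot comparisons no protection, and each is judged at 0.05 unadjusted.

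The wording also gives the last word to the t-test. The ANOVA already contains a one-degree-of-freedom test of the foot effect, which could be the deciding test at exactly the stated level, but the SAP does not use it that way. With the trigger and the comparisons both unspecified, they could be chosen after the data are seen.

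**Working it through.** **Inputs.** From the documents: level 0.05 (SAP; sidedness not stated, two-sided assumed); a 2 × 2 layout of foot and surface (SAP); both feet worn by the same participant (protocol). Assumed, because neither document gives them: n = 5, 10, 20; within-person correlation ρ between the two feet of 0, 0.4, 0.6, 0.8; surface effect of 0 to 3 SD; two follow-up foot tests, one per surface. The trigger was simulated as any of the three repeated-measures ANOVA effects reaching 0.05, with no true foot effect and 20,000 runs per setting.

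**1. The plan's own figure.** The 0.05 is an input, so there is nothing to reproduce. One foot test of correct size gives 1 − 0.95 = 0.05.

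**2. Two correctly sized tests, no protection.** If independent, 1 − 0.95² = 0.0975.

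**3. The planned unpaired test.** The true variance of a foot difference is proportional to 2(1 − ρ), but the unpaired test assumes 2. In large samples each test therefore has true size 2 × [1 − Φ(1.96/√(1 − ρ))], and two independent tests give 1 − (1 − size)².

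| ρ | 1.96/√(1 − ρ) | Size of one test | Two tests |
|---|---|---|---|
| 0 | 1.960 | 0.0500 | 0.0975 |
| 0.23 | 2.234 | 0.0255 | 0.050 |
| 0.4 | 2.530 | 0.0114 | 0.023 |
| 0.6 | 3.099 | 0.0019 | 0.004 |

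Break-even is near ρ = 0.23. The small-sample simulation with a 3 SD surface effect agrees in direction and runs somewhat higher: 9.7–10% at ρ = 0, 2.8–3.9% at 0.4, 0.6–1.9% at 0.6, and 0.5% or less at 0.8.

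**4. How often the trigger opens with no foot effect.** The ranges are over the correlation settings.

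| Surface effect | n = 5 | n = 10 | n = 20 |
|---|---|---|---|
| 0.5 SD | 22–37% | – | 61–95% |
| 1 SD | 47–82% | 83–100% | 99–100% |
| 3 SD | almost always | almost always | 100% |

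**5. The same trigger with paired tests.** The chance of at least one false foot finding in the two per-surface tests is:

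- 5.8–6.4% with no surface effect (n = 20);
- about 8.7–10% with a 3 SD surface effect;
- about 4–6% if only a foot or foot-by-surface effect opens the tests, and 2.4–3.7% with Holm added.

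The rise from about 6% to 9–10% is the part due to the surface factor opening the follow-up.

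**The case against.** **The trigger can be read more kindly.** The word for any difference sits in the sentence on the ANOVA's purpose. The follow-up sentence may mean that the t-test examines whichever effect was found, so that a surface effect leads only to a surface t-test. That reading is possible. The SAP does not state it, however, and nothing in the text excludes the other. The ambiguity is itself what needs removing.

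**A reader might infer that the plan as written doubles the 0.05.** The documents do not support this. The doubling needs two tests that each have true size 0.05, and the planned test is unpaired on people measured with both feet. Unless one person's two times are nearly uncorrelated (ρ below about 0.23), the planned tests stay under 0.05, and the likelier harm is lost power. This part of the objection stands in full.

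**A reader might infer that gravel will nearly always open the follow-up.** That needs an effect size and a sample size that the documents do not give. With 0.5 SD and n = 5, the trigger opens in only 22–37% of runs.

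**The number of tests is not given.** The SAP speaks of a t-test in the singular. One correctly sized foot test gives 0.05; two is the natural reading of four conditions, but it remains an assumption. Comparing one foot on level with the other on gravel, which could be significant from surface alone, is not proposed anywhere. It is merely not ruled out.

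What remains is that the low error of the planned test is a by-product of a separate mistake. Correcting that mistake alone would expose the trigger.

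**Conclusion.** The concern holds in a limited form. The SAP leaves the follow-up untied to the foot effect and lets an unadjusted t-test decide, so the foot question is not tested at the stated 0.05. The direction of the departure depends on the test used:

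- **Unpaired, as planned:** usually below 0.05, about 2–4% at ρ = 0.4 and lower at higher correlation. It approaches 10% only if the two measurements on one person are uncorrelated.
- **Paired, with the trigger unchanged:** up to about 9–10% for two per-surface tests when the surface effect is large.

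These figures rest on assumed n, correlation, surface effect and number of tests. That a surface effect can open foot comparisons follows from the SAP's wording alone, which does not exclude it. This should be fixed, in the same revision as the unpaired test.

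**What to change.** Replace the follow-up sentence in the Statistical Plan with:

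> The confirmatory test is the 1-df within-participant foot effect in the repeated-measures ANOVA, at 0.05. Foot comparisons on each surface are paired contrasts, made only if the foot effect or the foot-by-surface interaction is significant, Holm-adjusted over the two, and reported as supportive; a significant interaction without a foot effect is not a confirmatory foot claim. A surface effect alone triggers no foot comparison, and one foot on level is not compared with the other foot on gravel.

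Two parts of this wording are essential. The contrasts must become paired at the same time: the restricted trigger plus Holm on unpaired tests gives an error of 1% or less at correlations of 0.4 and above, which adds strictness to a test that is already too conservative. The per-surface results must be supportive: if a foot claim could be made either through the foot effect or through the interaction followed by Holm, the chance of a false claim with paired tests was 5.6–6.7% in the settings run.

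The cost is a few sentences of SAP text and no new data. The downside is that the per-surface tests become slightly stricter and carry only supportive weight.

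### The follow-up foot comparison runs only after a significant ANOVA and yields only another verdict at 0.05; the SAP commits to no foot difference in seconds and no confidence interval

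*SAP*

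**What the plan says.** The SAP is a single paragraph headed Statistical Plan. Its two-way ANOVA "will be used to analyze the dependent variable, completion time in seconds". The factors are given as follows: "The independent variables being analyzed include stubby feet compared with the Sidekicks and a level surface compared to gravel". Each has two levels, and foot type is one of them.

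The purpose of the ANOVA is stated as a test: "The two-way ANOVA is used to determine whether there are any significant differences between the mean values of the independent groups". The next step is conditional and is also a test: "If a significant difference is detected an unpaired t-test will be implemented to determine if statistical significance exists". The criterion is given once: "A probability value of 0.05 will be set at the level of statistical significance".

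The secondary variables (cadence, velocity, step and stride length, pelvic angles) are named with no separate method. Of the remaining scales the SAP says only: "The balance confidence scale and RPE scale will be compared across independent variables". That comparison is not made conditional on the ANOVA.

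Neither document names a mean difference, an effect size, a confidence interval, a sample size, a power, a target difference or an SD. The Study Protocol has each participant use both foot types and averages three walks per condition. The data needed for a within-participant difference on each surface will therefore exist.

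**The concern.** The trial compares two types of prosthesis, so the useful answer is how many seconds faster or slower a participant walks on one than on the other, on level ground and on gravel. The written procedure asks whether there is a significant difference and, if so, asks again. It never asks how large the difference is or how precisely it is known.

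This matters most after a non-significant ANOVA. The procedure then stops, and a study that has ruled out any difference worth having looks the same as one too small to rule out anything. With no planned sample size or power in either document, a reader has nothing else in the plan from which to tell the two apart. After a significant ANOVA, the only further product is a second verdict.

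Making the t-test paired would not cure this. The condition and the missing estimate would both remain.

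**Working it through.** The plan gives no sample size, power or effect to reproduce, so the size of the problem can only be illustrated over an assumed range.

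**Inputs**
- Significance level 0.05, from the SAP. Sidedness is not stated; two-sided is assumed.
- The same participants use both feet, with one averaged time per condition, from the Study Protocol. The natural foot comparison on one surface is therefore paired.
- Number of participants n: not stated. Assumed 5, 10 and 20.
- True foot difference: not stated. Assumed 0.5 SD of the paired differences.
- SD of the paired differences: not stated, so results are in SD units and cannot be converted to seconds.

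**Half-width of the 95% interval**, in SD of the paired differences: t(0.975, n−1)/√n.
- n = 5: 2.776/2.236 = 1.24
- n = 10: 2.262/3.162 = 0.72
- n = 20: 2.093/4.472 = 0.47

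**Chance of a non-significant paired test**: one minus the power from the noncentral t distribution with n−1 degrees of freedom and noncentrality 0.5√n.

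| n (assumed) | noncentrality | power | non-significant |
|---|---|---|---|
| 5 | 1.118 | 0.141 | about 86% |
| 10 | 1.581 | 0.293 | about 71% |
| 20 | 2.236 | 0.565 | about 44% |

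These rates are for a paired comparison on one surface. They are not the rates for the SAP's ANOVA, whose foot main effect pools the two surfaces, nor for its unpaired t-test.

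**What the interval adds.** Take n = 10 and two results that are both non-significant in this paired test. An observed difference of 0 has the interval −0.72 to 0.72 SD. An observed difference of 0.70 SD has the interval 0.70 − 0.72 = −0.02 to 0.70 + 0.72 = 1.42 SD. A plan whose only product is a verdict at 0.05 reports these identically. At n = 20, an observed difference of 0 has the interval −0.47 to 0.47 SD and so excludes the assumed 0.5 SD; at n = 10 the same observation does not. Only the interval shows that.

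**The case against.** Several points on the other side are fair.

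*Foot type is always tested.* A reader might infer that the plan compares the feet only when the ANOVA is significant. The SAP does not support that: foot is an ANOVA factor and its F test is run every time. Only the follow-up t-test is conditional. Nor is the follow-up wholly redundant, since the foot main effect pools the surfaces and does not give the difference on each one. What stands is that neither step is said to produce an estimate.

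*Silence is not refusal.* A reader might infer that a result of p ≥ 0.05 will be read as no difference, or that means will be withheld after a null ANOVA. Nothing in either document says so. SPSS can print means and intervals, and the ANOVA is described in terms of means. The supportable statement is narrower: the SAP does not commit to reporting or interpreting them.

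*The filter exaggerates the estimate.* A reader might infer that a foot difference estimated only after passing the filter will be badly inflated. That depends on which ANOVA effect opens it, and the SAP does not say. In simulations with n of 5, 10 and 20, a true foot difference of 0.5 SD on each surface and independent errors, the level-ground estimate after a significant ANOVA averaged:
- about 1.4, 1.3 and 1.1 times the truth if any effect may open the filter and there is no surface effect;
- about 1.6, 1.3 and 1.1 times if the foot effect itself must be significant;
- about 1.06, 1.00 and 1.00 times if an assumed surface effect of 1 SD can open it.

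The inflation ranges from modest to negligible except in very small samples, and the point does not rest on it.

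*The non-significance rates describe power, and an interval does not change them.* This is correct. The missing sample size is a separate matter. The rates show only how often a bare verdict could leave a reader without an answer, under assumed values. The remedy also replaces the unpaired test with within-participant differences, so it overlaps with the pairing question.

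**Conclusion.** The concern holds in a limited form. The SAP states a rule, not merely a gap: the direct follow-up comparison depends on a significant ANOVA, and its only stated product is another verdict at 0.05. Followed exactly, a non-significant ANOVA leaves no foot difference per surface, no interval, and so no measure of what the data exclude.

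Across the assumed 5 to 20 participants, the uncertainty left unreported would be 1.24 down to 0.47 SD of the paired differences either side of the estimate. A true 0.5 SD difference would be missed by a single-surface paired test in about 86% down to 44% of trials. Both the sample sizes and the 0.5 SD are assumptions, as is the two-sided test. The finding that no estimate or interval is planned depends on none of them.

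This is a reporting and estimation weakness that should be corrected in the plan. It does not show that the ANOVA omits the foot comparison or that the investigators would misread a null result.

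**What to change.** Replace the conditional unpaired t-test in the Statistical Plan with wording to this effect:

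- For completion time, whatever the ANOVA p-value, compute each participant's Sidekick-minus-stubby difference on level ground and on gravel, using the mean of the three walks in each condition.
- Report the mean difference in seconds with a 95% confidence interval for each surface.
- Report the gravel-minus-level contrast of these two differences, which is the foot-by-surface interaction, with its 95% confidence interval.
- Report the secondary variables in the same way on the surfaces where they are measured. Where only the level surface is used, as in the TUG test, the contrast between surfaces does not apply.
- State that conclusions will be drawn from the intervals.

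The cost is a few sentences of SAP text. No extra data, visits or participants are needed, and SPSS produces the intervals. The one downside is that a wide interval makes a small study look less decisive, which would be a fair reflection of what it can show.
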